## 1.0 STUDY OVERVIEW AND RATIONALE

This study is an investigator-initiated, prospective, open-label, randomized clinical trial of coffee abstention compared to continued caffeinated coffee consumption in patients with atrial fibrillation (AF). It will be conducted at multiple clinical sites in the United States, Australia, and Canada. The goal is to enroll and randomize two-hundred (200) adult men and women.

AF is the most common, sustained heart rhythm disorder experienced by humans. Coffee is one of the most ubiquitously consumed substances worldwide. Given both the increasing population impact of AF and the widespread use of coffee in society, determining any benefit, risk, or lack of any effect of coffee on AF would be of great interest to physicians, scientists, and individual consumers.

Prior observational studies have evaluated the role of chronic coffee consumption and incident AF with varied results. [1-3] However, established notions exist that coffee and caffeine contribute to AF and/or trigger AF episodes. In a large study of symptomatic patients with paroxysmal AF, caffeine was reported as the second most common triggering factor in almost one-third of individuals.[4] Prior surveys of physicians have also suggested reductions in caffeine to assist with arrhythmias.[5] Conversely, professional society guidelines either do not discuss coffee or caffeine[6] or suggest they are unlikely to contribute based on recent studies.[7] Interestingly, observational studies generally suggest that caffeinated coffee has no association with AF, or even may be associated with a *lower* risk of AF.[8] [2, 3, 9]

A key limitation of existing data on the effects of coffee and caffeine on AF has been their observational nature. This trial thus seeks to assess the effect of random allocation to coffee abstinence compared to continued caffeinated coffee consumption in patients undergoing cardioversion for AF or atrial flutter, with patients being followed up for recurrent episodes of AF.

### 1.1. SCOPE FOR ANALYSIS

The trial analyses will assess the effect of coffee abstinence compared to continued caffeinated coffee consumption on AF recurrence in patients undergoing cardioversion.

## 2.0 STUDY AIMS AND ENDPOINTS

*Hypothesis: Coffee abstinence will result in a lower recurrence of AF following cardioversion compared to continued caffeinated coffee consumption* (mention of coffee for the SAP refers to caffeinated coffee; those randomized to avoid coffee were indeed randomized to avoid all coffee).

Primary endpoint:

- The number of people with first confirmed clinical recurrence of AF or atrial flutter, or device-detected recurrence lasting longer than 30 seconds, following cardioversion in the coffee abstinence group compared to the continued caffeinated coffee consumption group analyzed as a time-to-event outcome.

Secondary endpoints:

- Adverse events before censorship, including myocardial infarction, stroke or transient ischemic attack, heart failure exacerbation, syncope, emergency department visit, hospitalization, and death

- Atrial flutter and atrial fibrillation separately as incident outcomes

### **3.0 STUDY DESIGN**

This study is a multicenter, investigator-initiated, prospective, open-label, randomized clinical trial. After screening and eligibility has been determined, participants will be randomized after successful cardioversion. Follow-up visits will occur at: Month 1, Month 3, and Month 6. See the DECAF protocol for the schedule of evaluations, data sources, and windows for each of the study visits. Clinical sites will make every possible effort to ensure that each study visit is conducted within the specified window.

### **4.0 STUDY POPULATION**

The target population for this trial is adults in the United States, Australia, or Canada with AF.

Potential participants will be identified at each clinical site from lists of patients with a planned and/or scheduled direct current electrical cardioversion. Eligibility for the study will be confirmed, using the inclusion/exclusion criteria noted below, prior to randomization after successful cardioversion.

#### **INCLUSION CRITERIA**

Patients must meet **all** of the following to be eligible:

1. Men or women ≥ 21 years of age
2. Sustained atrial fibrillation or atrial flutter (provided patient has history of atrial fibrillation)
3. Planned/scheduled direct current electrical cardioversion
4. Consumption greater than or equal to one cup of caffeinated coffee per day sometime in the past 5 years
5. Willing and able to comply with coffee abstinence or continuation of caffeinated coffee for at least 6 months
6. Life expectancy of at least 6 months
7. Willing and able to return and comply with scheduled follow up visits
8. Willing and able to provide written informed consent

#### **EXCLUSION CRITERIA**

Patients will be excluded if they meet **any** of the following:

1. Established allergy or adverse reaction to coffee
2. Stated inability to comply with coffee abstinence or continuation
3. Atrial fibrillation ablation in preceding 3 months or planned in the next 3 months
4. Recent cardiothoracic surgery in preceding 3 months
5. Pregnancy or desire to get pregnant within next 6 months.
6. Current enrollment in an investigation or study of a cardiovascular device or investigational drug that would interfere with this study
7. Any other criteria, which would make the patient unsuitable to participate in this study as determined by the Principal Investigator (e.g., an uncontrolled drug and/or alcohol addiction)

#### **4.1 ALLOCATION**

After successful cardioversion, participants will be randomized (1:1) to one of the two arms: coffee abstinence or continued caffeinated coffee consumption.

The DECAF study-wide allocation scheme will be created by a statistician prior to the start of the trial. Randomization will be performed with 1:1 with stratification across sites.

Sites will be instructed to randomize a participant as follows:

- After primary eligibility has been confirmed
- After all screening measures have been performed
- As soon as possible after successful cardioversion

Participants who completed primary eligibility and screening measures but did not have a successful cardioversion (such as due to inability to convert AF or documented early recurrence of AF prior to leaving the procedure room) will be excluded prior to randomization.

#### **4.2 BLINDING**

Due to the nature of the intervention, it is not practical to have participants blinded to their randomized allocation.

### **5.0 SAMPLE SIZE AND POWER CALCULATIONS**

The goal is to enroll a total of 200 participants (n=100 per treatment group) study-wide.

The sample size is based on the following assumptions: (1) a 50% incidence of AF recurrence; (2) 10% loss to follow-up; and (3) 0.05 two-tailed alpha level. Under these assumptions, a sample of 200 individuals randomized 1:1 to either coffee abstention or continued caffeinated coffee consumption will provide 80% power to detect a 1.63 times increased hazard of AF between the groups.

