## 10.0 STATISTICAL METHODS

### 10.1 Sample Size and Randomization

The goal of this trial is the enroll a total of 200 participants (n=100 per treatment group).

Assuming a 0.05 two-tailed alpha level, 1:1 randomization scheme, 50% recurrence rate in the absence of coffee, and potential 10% loss to follow-up, a sample size of n=200 (100 per arm) will provide approximately 80% power to detect a 1.63 times increased hazard of AF recurrence between the groups.

The table below summarizes the minimum detectable relative hazards in Cox models with binary predictor, by baseline AF recurrence rate (RR) (rows) and Percent Lost to Follow up (LTFU) (columns)

	5% LTFU	10% LTFU
50% RR	1.68	1.69
60% RR	1.62	1.63

Randomization will be performed 1:1 with stratification across sites.

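### SAP 5.0 and Protocol 10.1 claim 80% power for a hazard ratio of 1.63 with 50% recurrence and 10% loss, but no two-sided reading of the 50% gives more than about 74%

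*Combined protocol and SAP*

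**What the plan says.** Protocol 10.1 sets 100 participants per arm, a two-sided 0.05 test and 1:1 allocation. It assumes a "50% recurrence rate in the absence of coffee, and potential 10% loss to follow-up", and concludes that power is approximately 80% for a hazard ratio of 1.63. Directly below is a table of minimum detectable hazard ratios, "by baseline AF recurrence rate (RR) (rows) and Percent Lost to Follow up (LTFU) (columns"). The 50% row reads 1.68 at 5% loss and 1.69 at 10%. The 60% row reads 1.62 and 1.63.

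SAP 5.0 gives the same size ("The goal is to enroll a total of 200 participants (n=100 per treatment group) study-wide"), the same loss, the same "0.05 two-tailed alpha level", the same 1.63 and the same 80%. Its recurrence assumption is a 50% incidence with no arm named: "The sample size is based on the following assumptions: (1) a 50% incidence of AF recurrence; (2) 10% loss to follow-up; and (3) 0.05".

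The hypothesis in SAP 2.0 is: "Coffee abstinence will result in a lower recurrence of AF following cardioversion compared to continued caffeinated coffee consumption". Abstinence is therefore the lower-hazard arm, and the hazard ratio above 1 describes continued coffee relative to abstinence.

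**The concern.** There are two faults in one statement.

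- **Rate and hazard ratio do not match.** Both sizing sentences pair 50% recurrence and 10% loss with 1.63, which the protocol's table assigns to 60% recurrence.
- **The arm is missing from the SAP.** The protocol ties the 50% to abstinence; the SAP does not tie it to any group. For a given hazard ratio, the expected number of events, and so the power, depends strongly on whether 50% describes the better arm, the whole trial or the worse arm.

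The SAP is the document the results will be read against. A reader of a null result who relies on its power statement would believe the trial had an 80% chance of detecting a hazard ratio of 1.63 under assumptions that do not give it that chance.

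**Working it through.** **Inputs.** 100 per arm, two-sided 0.05, 1:1 allocation, 10% loss, hazard ratio (HR) 1.63, 80% power (Protocol 10.1, SAP 5.0); six-month follow-up (SAP 6.1). Neither document states a dropout model. I assume exponential recurrence and exponential dropout over the six months, taken as one time unit, and show the alternative.

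**Formulas.**
- Events needed (Schoenfeld): 4(1.960 + 0.842)² / (ln HR)².
- Power: Φ(½ √events × ln HR − 1.960).
- Risk in the worse arm: 1 − (1 − p)^HR, where p is the risk in the better arm.
- Expected events per arm: 100 × λ/(λ+μ) × [1 − e^−(λ+μ)], with λ = −ln(1 − arm risk) and μ = −ln(0.90) = 0.105.

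**Step 1: reproduce the protocol table.** The HR detectable with 80% power, by the group to which the row rate is assigned:

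| Row rate, loss | Printed | Rate on abstinence | Rate overall | Rate on coffee |
|---|---|---|---|---|
| 50%, 5% | 1.68 | 1.681 | 1.76 | 1.88 |
| 50%, 10% | 1.69 | 1.690 | 1.77 | 1.89 |
| 60%, 5% | 1.62 | 1.621 | 1.68 | 1.76 |
| 60%, 10% | 1.63 | 1.629 | 1.69 | 1.77 |

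Of these three assignments, only the abstinence arm reproduces the table, and it does so in every cell.

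**Step 2: events needed.** HR 1.63: 31.4 / 0.4886² = 131.5, so 132. HR 1.69: 31.4 / 0.5247² = 114.0, or 115 rounded up.

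**Step 3: the claim as printed (50% on abstinence, HR 1.63, 10% loss).**
- Coffee-arm risk: 1 − 0.5^1.63 = 67.7%.
- Abstinence events: 100 × 0.693/0.798 × (1 − 0.450) = 47.7.
- Coffee events: 100 × 1.130/1.235 × (1 − 0.291) = 64.9.
- Total 112.6, against 132 needed.
- Power: Φ(½ × 10.61 × 0.4886 − 1.960) = Φ(0.632) = 73.6%.

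A log-rank simulation of 10,000 trials gave 73.8%. If the lost 10% contribute no events: 90 × (0.500 + 0.677) = 105.9 events and 71.0%. With no loss at all: 117.7 events and 75.5%, still short of 80%.

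**Step 4: the other readings at HR 1.63, 10% loss.**

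| Where the 50% sits | Abstinence / coffee risk | Events | Power | Power if losses give no events |
|---|---|---|---|---|
| Abstinence arm | 50.0% / 67.7% | 112.6 | 73.6% | 71.0% |
| Overall | 41.6% / 58.4% | 95.5 | 66.6% | 64.0% (90 events) |
| Coffee arm | 34.6% / 50.0% | 80.7 | 59.3% | 56.8% |

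**Step 5: pairings that do give 80% (10% loss).**
- 50% on abstinence, HR 1.69: coffee risk 1 − 0.5^1.69 = 69.0%; 47.7 + 66.2 = 113.9 events; 80.0%.
- 60% on abstinence, HR 1.63: coffee risk 1 − 0.4^1.63 = 77.5%; 57.4 + 74.5 = 131.9 events; 80.1%.
- 50% overall: 95.5 events; detectable HR = exp(2 × 2.802 / √95.5) = 1.77.

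**The case against.** **The SAP sentence is shorthand for the protocol's.** It repeats the same size, alpha, loss and hazard ratio, and never says the 50% is pooled, so the protocol's definition may be meant to carry over. That is a fair reading. It does not rescue the claim, because at 1.63 the protocol's own wording gives 71–74%. It does mean that the overall-rate figure of 64–67% is one reading and not the SAP's established meaning.

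**Putting the base rate on the lower-hazard arm is legitimate.** This stands. A reader might infer that the 50% was placed on the wrong arm because abstinence is the intervention. The documents do not support that: a hazard ratio above 1 needs a lower-hazard reference, Protocol 10.1 names it, and the table is correct on that basis.

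**The SAP's rewording caused the shortfall.** A reader might infer this too. It does not hold, because the mismatch between 50% and 1.63 is already in Protocol 10.1. Dropping the arm adds ambiguity to an existing error.

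**Another calculation might give 80%.** A one-sided 0.05 test with 50% on abstinence gives about 81–83% at 10% loss, but both documents say two-tailed. Applying 1.63 as a ratio of risks (coffee risk 0.50 × 1.63 = 81.5%) gives 131.5 events and 80% with no loss. With the 10% removed it gives 90 × 1.315 = 118.4 events and 76%, and that method does not reproduce the table.

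**Planning power does not decide what a null result excludes.** Correct: the Cox estimate and its confidence interval (SAP 6.1) do that. This limits the consequence but does not make the printed power right.

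**Conclusion.** The power statement is wrong as written in both documents. With 50% recurrence, 10% loss, 200 participants and a two-sided 0.05 test, power at a hazard ratio of 1.63 is 6 to 9 points below the claimed 80% on the most favourable reading, 13 to 16 points below if 50% is overall, and 21 to 23 points below if it is the coffee-arm rate. The direct cause is that 1.63 belongs to the table's 60% row. The missing arm in SAP 5.0 is a second, smaller fault, and it would remain after the hazard ratio was corrected: 50% overall with 1.69 gives 73% (70% if losses contribute no events), not 80%.

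The documents do not show whether the rate or the hazard ratio was miscopied. They also do not support concluding that the trial must be enlarged: the table itself is sound, and the fault lies in the sentence drawn from it.

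The result rests on proportional hazards and on a dropout model inferred from its match to the table. Counting no events from lost participants lowers power by 2 to 3 points throughout.

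**What to change.** Keep n=200. Use identical wording in SAP 5.0 and Protocol 10.1, name the arm to which the recurrence rate applies, and make rate and hazard ratio agree. Any one of these is consistent:

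1. 50% in the abstinence arm, detectable hazard ratio 1.69 at 80% power (implies about 69% recurrence on continued coffee, about 114 events).
2. 60% in the abstinence arm, detectable hazard ratio 1.63 at 80% power (implies about 78% on continued coffee, about 132 events).
3. 50% in the abstinence arm with hazard ratio 1.63, and power stated as about 73%.

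If the SAP does intend 50% as the overall rate, state a detectable hazard ratio of about 1.77 (about 95 events). In each case say how loss to follow-up was handled.

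The cost is one or two sentences in each document. Under options 1 and 3, or with 50% overall, the stated sensitivity becomes less favourable; option 2 rests on a higher assumed recurrence rate. No participants, data or procedures are added, and the analysis is unchanged.

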### **6.0 STATISTICAL METHODS**

All analyses will be conducted upon completion of data collection and database lock. No interim analyses are planned.

The primary analysis will be by intention-to-treat (ITT), according to randomized allocation, without regard to participant compliance with this randomized allocation. Every attempt will be made to collect data for both primary and secondary endpoints until the end of the six month follow-up period for all randomized participants, and all data will be included as part of the primary ITT analysis.

Although substantial crossover is not anticipated, as treated and per protocol analyses will be conducted if failure to comply with the randomized allocation occurs in more than 10% of all participants or if there is a significantly different proportion of assignment adherence in one group compared to the other. The per protocol analyses will be restricted to a sub-sample excluding all the protocol violators, and adjust for any baseline factors that are imbalanced ( $P<0.1$ ) in the per-protocol sub-sample.

Patient baseline characteristics will be summarized overall and by randomization assignment. Continuous variables will be summarized using means and standard deviations (SD) for normally

distributed measures or medians and quartiles for non-normally distributed measures. Categorical variables will be summarized using contingency tables that display counts and percentages.

All tests will be two-sided with a 0.05-level of significance. Adjustment for multiple comparisons will not be used.

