### 10.2 Intention-to-Treat (ITT)

The main intention-to-treat (ITT) analysis set will include all randomized participants, whether or not they are compliant with the treatment allocation for this trial. Every attempt will be made to collect data until the end of the follow-up period for all randomized participants and these data will be included as part of the main ITT analysis. The analyses for the primary objective will be performed using the ITT dataset.

Although substantial crossover is not anticipated, as treated and per protocol analyses will also be conducted if failure to comply with allocated treatment assignments occurs in more than 10% of cases or if there is a significantly different proportion of assignment adherence in one group compared to the other.

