## **6.1 PRIMARY ENDPOINT ANALYSIS**

The primary endpoint, defined as the clinical recurrence of AF or device-detected AF lasting longer than 30 seconds, will be analyzed as a time-to-event outcome. Follow-up time for participants who do not experience the primary endpoint will be censored at the time of study withdrawal or end of study (month 6). Kaplan-Meier plots will be used descriptively to compare the survival distributions of the primary endpoint by randomization arm. Cox proportional hazards regression models including the randomization assignment will be used to formally analyze the primary endpoint (AF recurrence). These models will also include study site, used in the randomization procedure as a stratification factor, and additionally baseline patient characteristics in sensitivity analyses. Point estimates and Wald-based 95% confidence intervals and p-values will be reported. The primary ITT analysis will include all participants regardless of compliance with randomized allocation.

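### The as-treated analysis has no confounder adjustment, so if adherence tracks prognosis its hazard ratio can be biased in either direction; the per-protocol P<0.1 screen is mainly a prespecification weakness

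*Combined protocol and SAP*

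**What the plan says.** SAP 6.0 makes intention-to-treat primary: "The primary analysis will be by intention-to-treat (ITT), according to randomized allocation". It then adds two conditional analyses: "as treated and per protocol analyses will be conducted if failure to comply with the randomized allocation occurs in more than 10% of all participants". A significant difference in adherence between the arms is a second trigger. Protocol 10.2 carries the same triggers ("as treated and per protocol analyses will also be conducted") and gives no covariates for either analysis.

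The SAP's only adjustment rule for these analyses is in the sentence that follows the trigger, and that sentence concerns one of them. It opens: "The per protocol analyses will be restricted to a sub-sample excluding all the protocol violators". On covariates, its instruction is "and adjust for any baseline factors that are imbalanced", judged at P<0.1 within that subset. Nothing equivalent is written for as-treated.

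SAP 6.1 does mention covariates, but for a different model: "Cox proportional hazards regression models including the randomization assignment will be used to formally analyze the primary endpoint". Site enters that model, and "additionally baseline patient characteristics in sensitivity analyses". The baseline characteristics are not named. SAP 6.2 repeats the pattern for the secondary endpoints, again with randomized assignment as the exposure.

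**The concern.** An as-treated analysis compares people by what they did. In this open-label trial, what they did may depend on how ill they are or what they believe. Protocol 1.4 reports that almost a third of symptomatic patients with paroxysmal AF named caffeine as a trigger, so patients with more troublesome AF might give up coffee whatever their allocation. The reverse is also possible. An unadjusted as-treated hazard ratio would mix that selection with any effect of coffee.

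The trigger could plausibly be met. The protocol's change log gives patients' reluctance to abstain as the reason for shortening the study. Eligibility requires daily coffee only at some time in the past five years, so people who no longer drink it daily can be allocated to continue. The SAP tests everything at 0.05 without multiplicity adjustment, so nothing formal guards against a chance or selected as-treated finding.

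The per-protocol rule raises a lesser issue. It names no candidate list, so the model depends on which factors are tested and on what the data show.

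**Working it through.** **Plan's own figure.** The plan states none for these analyses. The assumptions in SAP 5.0 give the information available: 200 × 0.90 × 0.50 = 90 recurrences, if each lost patient contributes none.

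**Which text governs which model**

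| Analysis | Groups compared | Adjustment stated |
|---|---|---|
| ITT (SAP 6.1, 6.2) | randomized arms | site; unnamed baseline factors in sensitivity analyses |
| Per-protocol (SAP 6.0) | adherent patients only | factors with P<0.1 in that subset |
| As-treated (SAP 6.0) | actual coffee behaviour | none |

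**Expected bias by hand.** The inputs are assumptions; none comes from the documents. Coffee has no effect. One binary factor, present in 40%, multiplies the recurrence hazard by h. In arm A, 30% of patients with the factor and 10% without it switch behaviour. In arm B the two rates are reversed.

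- A: 12 of 40 with the factor and 6 of 60 without it switch. B: 4 of 40 and 18 of 60. Total 40/200 = 20%.
- Behaving as A: 28 + 4 = 32 of 104 have the factor (30.8%). Behaving as B: 36 + 12 = 48 of 96 (50.0%).
- Early hazard ratio, A versus B = [1 + (h−1)·0.308] / [1 + (h−1)·0.500].
- h = 2: 1.308/1.500 = 0.87. h = 3: 1.615/2.000 = 0.81. With the arm labels swapped: 1.15 and 1.24.
- With 40% and 10% switching (25% overall): 28 of 106 (26.4%) against 52 of 94 (55.3%). h = 2: 1.264/1.553 = 0.81. h = 3: 1.528/2.106 = 0.73.
- With 20% switching whatever the factor, both groups have 40% and the ratio is 1.

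**Simulation of these cases.** 2,000 trials each, no true effect, about 50% recurrence, 10% loss, Cox model with Wald test. Cells give the hazard ratio and the false-positive rate.

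| Switching by factor (overall) | h | As-treated, unadjusted | As-treated, adjusted | Per-protocol, unadjusted | Per-protocol, P<0.1 rule | Rule selects factor |
|---|---|---|---|---|---|---|
| 30/10% (20%) | 2 | 0.88, 10.0% | 1.00, 5.2% | 0.92, 6.6% | 0.98, 5.4% | 47% |
| 40/10% (25%) | 2 | 0.82, 15.4% | 1.00, 5.4% | 0.88, 8.2% | 0.99, 5.6% | 78% |
| 40/10% (25%) | 3 | 0.73, 31.6% | 1.00, 5.2% | 0.81, 13.0% | 0.98, 4.6% | 78% |
| 20/20% (20%) | 2 | 1.01, 4.6% | 1.01, 4.6% | 1.01, 4.2% | 1.01, 4.1% | 9% |

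The unadjusted hazard ratios agree with the hand calculation. ITT false positives were 4.8–5.1% in the first three rows and 4.0% in the last.

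**Milder inputs.** A second set assumed 13–20% non-adherence, nearer the trigger, with h from 1.5 to 3 and the bias running the other way. Unadjusted as-treated gave about 1.04–1.24 with 5–17% false positives, and adjustment returned about 1.00 and 5–6%. Per-protocol with the P<0.1 rule gave about 1.01–1.04 with error near 5%. This is the range to quote; the 25% rows are harsher than the argument needs.

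**The screen.** For 40% versus 30% with 90 per arm, the pooled standard error is √(2·0.35·0.65/90) = 0.0711 and the unpooled is √(0.24/90 + 0.21/90) = 0.0707. Power at P<0.1 is Φ[(0.100 − 1.645·0.0711)/0.0707] = Φ(−0.24) = 41%. With 80 and 60 it is 33%. The screen therefore often misses a 10-point imbalance, yet the table shows little harm, because it tends to act in the trials where the imbalance is large.

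**The case against.** The strongest reply is that little depends on these analyses. They run only if triggered, the plan does not expect substantial crossover, and no text lets them replace ITT. That stands. A reader might infer that the plan would rest its conclusion on them if adherence were poor; SAP 6.0 and 6.1 rule this out by keeping ITT primary regardless of compliance.

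A reader might also infer that both non-randomized comparisons are likely to show a coffee effect that is only selection. The per-protocol half of that is not supported. Under the P<0.1 rule the residual bias was small and the error near nominal in both sets of simulations. Replacing the screen is justified by prespecification more than by bias.

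Third, the documents contain no figure linking adherence to prognosis, and at the mild end of the range there is no inflation. That also stands: the size is conditional, and without the link there is no bias.

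Fourth, SAP 6.1 and 6.2 already plan baseline-adjusted sensitivity models. These do not close the gap, because their exposure is randomized assignment and their covariates are unnamed.

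Finally, the simulated recovery is partly circular, since the only confounder is measured and then adjusted for. Unmeasured factors, post-baseline reasons for non-adherence, and the undefined terms for as-treated and protocol violator all remain.

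**Conclusion.** The point holds for the as-treated analysis. As written, it is a non-randomized comparison with no stated adjustment. If adherence depends on prognosis, the null hazard ratio is about 1.04–1.24 with 5–17% false positives, for an assumed confounder hazard ratio of 1.5–3 and 13–20% non-adherence. Harsher assumptions with selection the other way gave values down to 0.73, so neither the sign nor the size can be corrected by judgement afterwards. Adjusting for the factor removes the bias to the extent that the factor is measured at baseline.

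For the per-protocol analysis the defect is a data-dependent model with a small residual bias. The primary ITT result is unaffected, so this concerns the credibility of supportive analyses and not the trial's main conclusion.

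**What to change.** In SAP 6.0, state that the as-treated Cox model adjusts for site and a short, fixed set of prognostic baseline factors, whatever their P values. Use the same set for the per-protocol model in place of the P<0.1 screen. Label both as supportive, non-randomized comparisons.

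Candidates can come from items collected at baseline in Protocol Table 2: age, sex, BMI, entry rhythm, baseline antiarrhythmic drug, and baseline coffee and alcohol intake. Heart failure and prior ablation would be natural additions, but Table 2 lists only a detailed medical history, so confirm first that they are CRF fields.

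The change needs a sentence or two and no new visits. It does cost degrees of freedom. Counting each factor as one term, the seven named, two site terms and the exposure make 10 parameters. That is 90/10 = 9 events per parameter as-treated, and (90 × 0.90)/10 = 8.1 per-protocol if 10% are excluded. Adding heart failure and ablation makes 12 parameters, or 7.5 and 6.75, so other factors should be dropped to make room. Unmeasured and post-baseline selection would remain and should be acknowledged when the results are reported.
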